#### Figure 1-1 Study design

## 1.2 Study objectives and endpoints

#### 1.2.1 Primary objective

The primary objective of this study is to further evaluate the safety and tolerability of ribociclib in combination with letrozole in men and pre/postmenopausal women with HR+, HER2- aBC who received no prior hormonal therapy for advanced disease.

To evaluate the primary objective the number (%) of patients who experienced adverse events (AEs) will be calculated for the following AE categories:

- Any AEs
- Grade 3/4 AEs
- Serious Adverse Events (SAEs)
- AEs of Special Interest (Neutropenia (including febrile neutropenia), QT prolongation, hepatobiliary AEs)
- AEs leading to discontinuation
- AEs leading to dose reduction or dose interruption
- Deaths

#### 1.2.2 Secondary objective

The secondary objective of this study is to assess the clinical efficacy and patient-reported outcomes (PRO) of ribociclib + letrozole (+ goserelin) in Full Analysis Set.

The following efficacy endpoints as defined by RECIST1.1 will be used in the evaluation of secondary objectives:

- Time-to-Progression (TTP) based on investigators' assessment
- Overall Response Rate (ORR) for patients with measurable disease at baseline
- Clinical Benefit Rate (CBR) (including patients with complete response (CR), partial response (PR), (stable disease (SD)/Non-CR/Non-PD)>24 weeks)

In addition, PRO will be assessed using Functional Assessment of Cancer Therapy – Breast (FACT-B) instrument. (See Section 2.11)

During Extension Phase, frequency and severity of AEs & SAEs will be summarized.

The proportion of patients with clinical benefit as assessed by investigator will be reported at each scheduled visit during Extension Phase.

Table 1-1Objectives and related endpoints

Objective	Endpoint
Primary	
To evaluate the safety and tolerability of ribociclib + letrozole in men and pre/postmenopausal women with HR+, HER2- aBC who received no	
 
Number (%) of patients who experienced AEs, Grade 3/4 AEs & SAEs during treatment with ribociclib + letrozole
 

Novartis	Confidential	Page 13
SAP	22-Feb-2022 (1:27)	CLEE011A2404
Objective	Endpoin	t
prior hormonal therapy for advanced dis	ease	
Note: Throughout this document, perime and premenopausal status are grouped and referred as "Premenopausal" Secondary To assess the clinical efficacy and patien reported outcomes of ribociclib + letrozo patient population as described above	enopausal together nt • le in the •	Time-to-Progression (TTP) (RECIST 1.1), based on investigators' assessment Overall response rate (ORR) as defined by RECIST 1.1 for patients with measurable disease Clinical Benefit Rate (CBR) as defined by RECIST 1.1 (including patients with CR, PR, SD/Non-CR/Non-PD>24 weeks) Patient Reported Outcome (PRO) using
		FACT-B questionnaire
To evaluate long-term safety of ribociclik letrozole during Extension Phase	•	Frequency and severity of AEs & SAEs during Extension Phase
To evaluate clinical benefit of ribociclib + as assessed by investigator during Exter Phase	letrozole     nsion	Proportion of patients with clinical benefit as assessed by investigator during Extension Phase

# 2 Statistical methods

## 2.1 Data analysis general information

Novartis and/or a designated Contract Research Organization (CRO) will perform all analyses. SAS version 9.4 or later software will be used to perform all data analyses and to generate tables, figures and listings.

## 2.1.1 Data included in the analysis

The analysis cut-off date for the final analysis of the Core Phase will be established after all enrolled patients have completed at least 18 months of treatment or have discontinued study. Interim analyses (IA) are planned to be performed periodically. The first IA planned to be performed about 12 months after FPFV, and periodically if needed to fulfill regulatory requests, safety updates, or for publication purposes. All statistical analyses will be performed using all data collected in the database up to the data cut-off date. All data with an assessment date or event start date (e.g. vital sign assessment date or start date of an adverse event) prior to or on the cut-off date will be included in the analysis. Any data collected beyond the cutoff date will not be included in the analysis and will not be used for any derivations.

Novartis	Confidential	Page 14
SAP	22-Feb-2022 (1:27)	CLEE011A2404

Final analysis of the Extension Phase will be performed when all patients have been followed for 30 days after they have either prematurely discontinued or been discontinued from the study after completing treatment as per protocol.

All events with start date before or on the cut-off date and end date after the cut-off date will be reported as 'ongoing'. The same rule will be applied to events starting before or on the cutoff date and not having documented end date. This approach applies, in particular, to adverse event and concomitant medication reports. For these events, the end date will not be imputed and therefore will not appear in the listings.

## 2.1.2 General analysis conventions

**Pooling of centers:** Unless specified otherwise, data from all study centers will be pooled for the analysis. Protocol deviations, number of patients in analysis populations and discontinuations from study treatment will be summarized by center.

**Qualitative data** (e.g., gender, race, etc.) will be summarized by means of contingency tables; a missing category will be included as applicable. Percentages will be calculated using the number of patients in the relevant population or subgroup as the denominator.

**Quantitative data** (e.g., age, body weight, etc.) will be summarized by appropriate descriptive statistics (i.e. mean, standard deviation, median, minimum, and maximum).

## 2.1.3 General definitions

#### Investigational drug and study treatment

**Investigational drug**, will refer to the ribociclib (LEE011) only. Whereas, **study treatment** will refer to ribociclib + letrozole + goserelin/leuprolide (if applicable).

The term investigational treatment may also be referred to as **study treatment** which is used throughout in this document.

## Date of first administration of investigational drug

The date of first administration of investigational drug is defined as the first date when a nonzero dose of investigational drug is administered and recorded on the Dosage Administration Record (DAR) Electronic Case Report Form (eCRF).

## Date of last administration of investigational drug

The date of last administration of investigational drug is defined as is the last date when a nonzero dose of investigational drug is administered and recorded on DAR eCRF. The date of last administration of investigational drug will also be referred as end of investigational drug.

## Date of first administration of study treatment

The date of first administration of study treatment is derived as the first date when a nonzero dose of any component of study treatment was administered as per the Dosage Administration eCRF. (Example: if 1st dose of ribociclib is administered on 05-Jan-2015, and 1st dose of letrozole is administered on 03-Jan-2015, then the date of first administration of study

Novartis	Confidential	Page 15
SAP	22-Feb-2022 (1:27)	CLEE011A2404

treatment is on 03-Jan-2015). The date of first administration of study treatment will also be referred as *start of study treatment*.

#### Date of last administration of study treatment

The date of last administration of study treatment is derived as the last date when a nonzero dose of any component of study treatment was administered as per Dose Administration eCRF. (Example: if the last ribociclib dose is administered on 15-Apr-2014, and the last dose of letrozole is administered on 17-Apr-2014, then the date of last administration of study treatment is on 17-Apr-2014).

## Study day

The study day, describes the day of the event or assessment date, relative to the reference start date.

The study day is defined as:

- The date of the event (visit date, onset date of an event, assessment date etc.) reference start date + 1 if event is on or after the reference start date;
- The date of the event (visit date, onset date of an event, assessment date etc.) reference start date if event precedes the reference start date.

The reference start date for all assessments (safety, efficacy, PRO, etc) is the start of study.

#### Time unit

A year length is defined as 365.25 days. A month length is 30.4375 days (365.25/12). If duration is reported in months, duration in days will be divided by 30.4375. If duration is reported in years, duration in days will be divided by 365.25.

#### Baseline

For safety and efficacy evaluations, the last available assessment on or before the date of start of study treatment is defined as "baseline" assessment.

In rare cases where multiple measurements meet the baseline definition, with no further flag or label that can identify the chronological order, then the following rule should be applied: If multiple values are from the same laboratory (local) or collected for Electrocardiograms (ECGs) or vital signs, then the last value should be considered as baseline.

If patients have no value as defined above, the baseline result will be missing.

#### On-treatment assessment/event and observation periods

The overall observation period will be divided into three mutually exclusive segments:

1. pre-treatment period:

Core Phase: from day of patient's informed consent to the day before first administration of study treatment.

Extension Phase: Not applicable.

#### 2. on-treatment period:

Core Phase: For patients who discontinue after the Core Phase treatment, on-treatment period is defined as from date of first administration of study treatment to 30 days after date of last actual administration of any study treatment (including start and stop date). For patients who transition to the Extension Phase, on-treatment period is defined as from date of first administration of study treatment to the date of last actual administration of study treatment to the date of last actual administration of study treatment to the date of last actual administration of study treatment to the date of last actual administration of study treatment to the date of last actual administration of any study treatment in the Core Phase.

Extension Phase: from date after the first administration of study treatment in the Extension Phase to 30 days after date of last actual administration of any study treatment

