10.5.3 Safety objectives

10.5.3.1 Analysis set and grouping for the analyses

For safety analyses in the Core Phase, the Safety Set in Core Phase will be used. For safety analyses in the Extension Phase, the Safety Set in Extension Phase will be used. All listings and tables will be presented.

The overall observation period will be divided into three mutually exclusive segments:

1. pre-treatment period:

Core Phase: from day of patient's informed consent to the day before first administration of study treatment.

Extension Phase: Not applicable.

2. on-treatment period:

Core Phase: For patients who discontinue after the Core Phase treatment, on-treatment period is defined as the time from the date of first administration of study treatment to 30 days after date of last actual administration of any study treatment (including start and stop date). For patients who transition to the Extension Phase, on-treatment period is defined as the time from the date of first administration of study treatment to date of last actual administration of any study treatment to the Extension Phase.

Extension Phase: from date of the first administration of study treatment in the Extension Phase to 30 days after date of last actual administration of any study treatment

3. post-treatment period:

Core Phase: starting at day 31after last administration of study treatment for patients who discontinue after the Core Phase treatment without transitioning to the Extension Phase. Post-treatment period is not applicable for patients who transition to Extension Phase.

Extension Phase: starting at day 31 after last administration of study treatment in the Extension Phase.

The safety summary tables will include assessments from the on-treatment period, unless otherwise specified. Further details will be included in the Statistical Analysis Plan (SAP).

All safety data collected in the study will be listed regardless of the study period with data collected during the pre-treatment and post-treatment period flagged.

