#### 3. *post-treatment period*:

Core Phase: starting at day 31after last administration of study treatment for patients who discontinue after the Core Phase treatment without transitioning to the Extension Phase. Post-treatment period is not applicable for patients who transition to Extension Phase.

Extension Phase: starting at day 31 after last administration of study treatment in the Extension Phase.

Safety summaries (tables, figures) include only data from the on-treatment period with the exception of baseline data which will also be summarized where appropriate (e.g. change from baseline summaries). In addition, a separate summary for death including on treatment and post treatment deaths will be provided. In particular, summary tables for adverse events (AEs) will summarize only on-treatment events, with a start date during the on-treatment period (*treatment-emergent* AEs).

However, all safety data (including those from the post-treatment period) will be listed and those collected during the pre-treatment and post-treatment period will be flagged.

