# 4 Change to protocol specified analyses

No change from protocol specified analysis was made.

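### The SAP opens the Extension on-treatment period one day later than the protocol, so adverse events starting on the first Extension dosing day usually fall outside both phases' treatment-emergent tables.

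*SAP*

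**What the plan says.** SAP section 2.1.3 states that "The overall observation period will be divided into three mutually exclusive segments": pre-treatment, on-treatment and post-treatment. For patients who move into the Extension Phase:

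- **Core on-treatment** runs from the first dose "to the date of last actual administration of any study treatment in the Core Phase". There is no 30-day tail.
- **Core post-treatment** does not exist: "Post-treatment period is not applicable for patients who transition to Extension Phase".
- **Extension pre-treatment** does not exist: "Extension Phase: Not applicable".
- **Extension on-treatment** is defined as "Extension Phase: from date after the first administration of study treatment in the Extension Phase" and runs to 30 days after the last dose.

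The same section says that the adverse event tables "will summarize only on-treatment events, with a start date during the on-treatment period". SAP section 2.8.6 applies the adverse event rules of sections 2.8.1 and 2.8.2 to the Extension Phase.

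Protocol section 10.5.3.1 gives a different opening date: "Extension Phase: from date of the first administration of study treatment in the Extension Phase". SAP section 4 says "No change from protocol specified analysis was made".

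**The concern.** The two documents differ by one day on when the Extension on-treatment period opens, and the SAP does not acknowledge it. The lost day is one on which study treatment is given. It is also inconsistent with the rest of the SAP: a single Extension dose puts a patient in the Safety Set in Extension Phase (section 2.2.4), and the Core on-treatment period includes its own first dosing day.

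At stake are the Extension counts of adverse events, serious adverse events and adverse events of special interest, which serve the secondary long-term safety objective. An error of this kind can only reduce those counts. The Core counts, which are the primary endpoint, do not depend on this wording.

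**Working it through.** The plan states no figure to reproduce here, so the check sets the windows side by side and counts days.

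**Notation.** C is the date of the last Core dose of any component, E the date of the first Extension dose, and L the date of the last Extension dose.

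**Windows for a patient who transitions.**

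- Core on-treatment, SAP 2.1.3: first dose to C.
- Extension on-treatment, SAP 2.1.3: E + 1 to L + 30.
- Extension on-treatment, protocol 10.5.3.1: E to L + 30.
- Core post-treatment and Extension pre-treatment: none.

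**Coverage of the transition days.** The documents do not report transition intervals, so the gaps below are assumed.

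| Gap E − C (days) | SAP: day E falls in | SAP: uncovered days | Protocol start date: day E falls in | Protocol start date: uncovered days |
|---|---|---|---|---|
| 0 | Core only | none | Core and Extension | none |
| 1 | neither | E | Extension | none |
| 2 | neither | E − 1 and E | Extension | E − 1 |
| 7 | neither | E − 6 to E | Extension | E − 6 to E − 1 |

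Day E is uncovered under the SAP for every gap except zero. The difference between the two start dates is exactly one day, E, whenever E is later than C. A gap of 1 is a plausible case: letrozole is taken daily without rest days (protocol 6.1.1), so a patient who continues without a break and starts Extension dosing the next day has E = C + 1. In that case the SAP wording is the only cause of any uncovered day.

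**Size.**

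- Patients exposed to the rule: 415 transitioned (protocol, Amendment 04 rationale).
- Lower bound, all with E = C: 0 × 415 = 0 patient-days.
- Upper bound, all with E later than C: 1 × 415 = 415 patient-days.
- Extension length: 18 months (protocol 4.3) × 30.4375 days per month (SAP 2.1.3) = 547.9 days.
- One day as a share of that: 1 / 547.9 = 0.18%. This takes a full 18 months and leaves out the 30-day tail, so it is illustrative.

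**From days to counts.** SAP 2.8.1 counts a patient once per adverse event category. A table entry therefore changes only if the patient's sole event in that category starts on day E. The documents give neither an onset rate for that day nor the number of patients with E = C, so the number of events lost cannot be calculated.

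**The case against.** The strongest defence is that the later start may be deliberate. The segments must be mutually exclusive, and if the last Core and first Extension doses share a date, the protocol wording puts that day in both windows. Opening the Extension a day later avoids this. That is a coherent purpose, but the SAP does not state it, and the rule drops day E for every patient whose first Extension dose comes later than the last Core dose. A same-date rule does the job without that loss.

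Three further points deserve weight:

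- **Protocol version.** The SAP says it is based on protocol v02, while the protocol text available is version 04. The last amendment log to list a change to section 10.5.3.1 is that of Amendment 02. The logs for Amendments 03 and 04 list none, apart from unspecified editorial changes. A mismatch with the current protocol is certain. That SAP section 4 was wrong against v02 is likely but not proven.
- **Text quality.** In the SAP text available, the Core sentence just before the disputed one contains a repeated phrase. The Extension sentence itself reads cleanly.
- **Other uncovered days.** Any days strictly between C and E are uncovered under both documents. This is true, but it is a separate feature, and it does not justify losing day E as well.

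It is also fair to say that the consequence is small. Affected events stay in the listings with a flag, the summary of all deaths is not limited to the on-treatment period, and no hypothesis is tested.

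**Conclusion.** The concern holds, as a minor one. Read as written, SAP 2.1.3 excludes the first Extension dosing day from every segment unless the last Core dose has the same date, and events starting that day are missing from both phases' treatment-emergent tables. The loss is 0 to 415 patient-days in total, at most one day per patient, and it can only lower the Extension counts. The lower and upper bounds correspond to all or none of the 415 patients having a shared date. No number of lost events is claimed.

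**What to change.** In SAP 2.1.3, replace the opening of the Extension on-treatment definition with the protocol's wording, "Extension Phase: from date of the first administration of study treatment in the Extension Phase". Add a same-date rule: when the last Core and first Extension doses fall on one date, an adverse event starting that day is assigned to one phase only, for example Core, whose window already contains the date. This keeps the segments mutually exclusive. Because the protocol has no such rule, record it in SAP section 4. The Core end boundary can stay as it is. The change does not cover days strictly between the two doses.

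The cost is one phrase and one sentence in the definition, a line in section 4, and one date condition in the programs. No new data are required.

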#### 3. *post-treatment period*:

Core Phase: starting at day 31after last administration of study treatment for patients who discontinue after the Core Phase treatment without transitioning to the Extension Phase. Post-treatment period is not applicable for patients who transition to Extension Phase.

Extension Phase: starting at day 31 after last administration of study treatment in the Extension Phase.

Safety summaries (tables, figures) include only data from the on-treatment period with the exception of baseline data which will also be summarized where appropriate (e.g. change from baseline summaries). In addition, a separate summary for death including on treatment and post treatment deaths will be provided. In particular, summary tables for adverse events (AEs) will summarize only on-treatment events, with a start date during the on-treatment period (*treatment-emergent* AEs).

However, all safety data (including those from the post-treatment period) will be listed and those collected during the pre-treatment and post-treatment period will be flagged.

#### Median follow-up of the study

Median study follow-up in this study will be calculated as (analysis cut-off date – median treatment start date  $\pm 1/30.4375$ , where 30.4375 is the average duration of a month in days. Median treatment start date is obtained by first sorting all patients in the FAS by the start date of study treatment, and then taking the date of median patient.

#### 2.1.4 Windows for multiple assessments

In order to summarize PRO measures/performance status/vital sign/other data collected over time (including unscheduled visits), the assessments will be time slotted. The following general rule will be applied in creating the assessment windows: If more than one assessment is done within the same time window, the assessment performed closest to the target date will be used. If 2 assessments within a time window are equidistant from the target date, then the earlier of the 2 assessments will be used. If multiple assessments on the same date then the worst case will be used. Data from all assessments (scheduled and unscheduled), including multiple assessments, will be listed.

Novartis	Confidential	Page 17
SAP	22-Feb-2022 (1:27)	CLEE011A2404

The following table provides an example how to define the time windows for Eastern Cooperative Oncology Group (ECOG) performance status (PS).

#### Table 2-1Time window for ECOG PS assessments

Assessment	Target day of assessment	Time interval
Baseline		≤ Day 1
Cycle 2 Day 1	29	Day 2 to Day 42
Cycle 3 Day 1	57	Day 43 to Day 70
Cycle 4 Day 1	85	Day 71 to Day 98
Cycle 5 Day 1	113	Day 99 to Day 126
Cycle 6 Day 1	141	Day 127 to Day 168
Cycle 8 Day 1	197	Day 169 to Day 224
Cycle 10 Day 1	253	Day 225 to Day 280
Cycle 12 Day 1	309	Day 281 to Day 350
Every 3 cycles thereafter		
Cycle k Day 1 (k = 15, 18, …, 36)	d=(k-1)*28+1	Day d-42 to Day d+41
End of Treatment		Assessment taken at the end of treatment visit

Time windows will be defined for descriptive summary of PRO data by visit and longitudinal data analysis. Data obtained at the end of treatment will be classified as other assessment in the corresponding time window. Note that only data collected under treatment (i.e. while the patient is treated) will be included in the time to definitive deterioration or longitudinal model analysis. Post-treatment data will be summarized separately. The end of treatment assessment will be included if collected within 30 days of the last dose intake. Time windows for PRO assessment (please refer to Table 2-1) is the same as the Time windows for ECOG PS assessment.

